### 3.2 Modification of ePOCT+ to improve accuracy and adapt to epidemiological changes

The ePOCT+ algorithm will be programmed in an electronic software support system that allows direct visualization and internal validation of the algorithm and subsequently deployed onto the users' devices. For this, a specific software solution is currently being developed which has three main components (**Figure 5**):

- The clinical algorithm management system (called medAL-creator) that will allow a clinician without any IT programming skills to manage, reference, modify and deploy different versions of the algorithm into a mobile device;
- The tablet- or PC-based application (called ePOCT+) that will contain the algorithm and be used for data acquisition by the HW (called medAL-reader), as well as automated capture of results from biosensors and rapid tests;
- The data management system that will receive and manage the data on a central server with a database.

**Figure 5:** General architecture of the software solution

In the second phase of the study, the algorithm will be modified according to trends in the collected data detected using ML or conventional statistical methods. The modifications will be specified and validated by clinical experts. Approved changes will then be integrated into the algorithm using medAL-creator and a new version of the ePOCT+ algorithm released. The new version will then be deployed onto the tablets or PCs of the relevant HWs (for example of a certain region where an epidemic is occurring) with a message explaining the rationale and evidence behind the change in the algorithm.

Modifications in the algorithms designed to perform as well as the original algorithm but using fewer/different resources will be implemented in the facilities they were designed to serve (for example, if certain facilities do not have access to a certain resource). Similarly, modifications designed to personalize the algorithm according to demographic characteristics, geography or season will be implemented on the target population for which they were intended.

### 3.3 Enhanced clinical competencies of health workers

#### *Supportive supervision*

To enable better supervision of HWs by the district medical team, we will also develop and deploy an electronic supervision tool called medAL-monitor. We will define clinical performance indicators, based on the data collected through ePOCT+, and integrate them into the electronic supervision tool. The tool will contain dashboards to visualize these indicators and monitor their spatial and temporal trends. The dashboards will be adapted to different users who would benefit from different indicators displayed to them in different ways. For example, at the district level, a dashboard will be enabled that will allow the DHMT to assess differential performance across health facilities and prioritize under-performing facilities for supportive supervision visits based on a set of criteria and indicator cut-off values. At the level of the HF in-charge or individual HWs, more granular information may be desired,

aggregated at the level of provider rather than facility. Here, the user may wish to view trends in their own performance on a daily, rather than monthly basis. medAL-monitor is intended to enable and encourage more frequent two-way communication between remote HWs and the DHMT team. The supervision tool will be pilot-tested with the DHMT and HWs before routine implementation.

### *e-Learning*

To continue improving providers' clinical skills throughout the project, e-learning modules will be developed and incorporated into ePOCT+. Such modules will help clinicians assess important clinical signs, especially pediatric danger signs (e.g. chest indrawing). First, we will perform an assessment of additional training needs among HWs. Next, we will screen available written materials, photos, sound clips, and video tutorials for suitability and adapt and translate them into the relevant languages for the Rwandan context, as needed. We will also develop additional training modules on clinical topics for which no training materials are available. The e-learning modules will then be pilot-tested among HWs and then deployed onto the clinicians' tablets and integrated with the ePOCT+ workflows.

The e-learning platform will be revised and upgraded throughout the project. Initially, a set of "information" buttons will be available for certain syndromes or clinical procedures so that the HW will be able to consult them in real-time. All of this content will also be curated in a reference library, which HWs will be able to consult at any time (e.g. in the afternoon after seeing patients). In the latter stages of the project, the e-learning process will be made more interactive, enabling the learner to answer questions and progress through the modules, reaching certain milestones. The approach will be further refined during the pilot stage, taking into consideration available platforms and certification processes for clinical skills required for IMCI that are currently available in Rwanda and in similar settings.

### **3.4 Enhanced monitoring and evaluation**

Beyond facilitating supportive supervision, the medAL-monitor/medAL-outbreak platform will also be used to enhance the M&E capacity in the intervention districts. Dashboards created with ePOCT+ data will enable the DHMT to monitor certain health indicators over time, be alerted if indicator values are higher than expected for a given month in a given location, suggesting a potential outbreak (or another change in the health system), and be able to decide if a response is needed.

As previously mentioned, different versions of the dashboard will be developed: for the HFs, the district level and the national level. Furthermore, the dashboards will have several pages for different types of health statistics, including but not limited to general information, main symptoms or syndromes, acute diseases, chronic conditions, and clinical management including treatment and referral. Specific indicators for self-audits (HF level), supervision (district level), M&E (district and national level) and syndromic disease surveillance (district and national level), will be available. Examples of important M&E indicators related to the impact of the present intervention that can all be stratified by geographical area, time period and age group are shown in **Table 3**.

It is important to note that medAL-monitor/medAL-outbreak at this stage is a concept rather than a specific IT platform. In fact, at the district level, the preliminary list of M&E indicators is intentionally similar to that available in the Rwandan HMIS. However, with the use of ePOCT+ in the intervention HFs, de-identified non-aggregated patient-level data serve as a data source for medAL-monitor/medAL-outbreak, rather than aggregated values based on fixed categories in the HMIS. This allows much more flexibility in how these data can be aggregated and displayed based on the various users' needs. All functionalities of HMIS (e.g. DHIS2) and other platforms in which indicator monitoring and alerts are enabled will be fully evaluated to ensure that the platform has useful and complementary, rather than redundant features. In the beginning of the project, all indicators consistent with HMIS in terms of their definitions will be transferred into HMIS to ensure continuity of national reporting in intervention facilities but also to serve as a basis for planning for future

interoperability. The MoH will thus be able to compare the data provided by the HMIS dashboard with that provided by the Clinivisor dashboard, for the 2 districts where ePOCT+ will have been implemented. If and when the MoH is ready to do so, interoperability between the two systems can be pursued.

**Table 3:** Examples of M&E indicators that will be possible to display in the medAL-monitor/medAL-outbreak dashboards based on ePOCT+ data

Consultations	
	
 
Number of outpatient consultations
 

Main indicators	
	
 
Number and % of deaths
 
Number and % of children referred to hospital
 
Number and % of children with malaria (severe and non-severe)
 
Number and % of children with bacterial pneumonia (severe and non-severe)
 
Number and % of children with diarrhea (severe and non-severe)
 
Number of measles cases
 
Number and % of children prescribed an antibiotic (by level of disease severity)
 
Number and % of children prescribed an antimalarial (by mRDT status)
 
% of final diagnoses made by HWs for which the appropriate treatment is prescribed
 

Danger signs	
	
 
% of children with at least one danger sign
 
% of children with each type of danger sign
 
% of children with at least one danger sign prescribed an antibiotic
 
% of children with at least one danger sign prescribed an antimalarial
 

Among children with cough/difficulty breathing	
	
 
Number and % of children with cough/common cold, viral pneumonia and bacterial pneumonia
 
Median and distribution of respiratory rate measurements
 
% of fast breathing among children with cough/difficult breathing
 
% of chest indrawing among children with cough/difficult breathing
 
Median and distribution of oxygen saturation measurements
 
% of hypoxemia among children with fast breathing or chest indrawing
 
% of children with bacterial pneumonia prescribed an antibiotic
 
% of children with viral pneumonia prescribed an antibiotic
 
% of children with cough/common cold prescribed an antibiotic
 
% of children with bacterial pneumonia prescribed the first line antibiotic
 

Among children with diarrhea	
	
 
% of children with diarrhea
 
% of dehydration among children with diarrhea
 
% of dysentery/persistent diarrhea among children with diarrhea
 
% of children with diarrhea prescribed ORS/zinc
 
% of children with diarrhea prescribed an antibiotic
 

Among children with fever/elevated temperature	
	
 
% of children with confirmed versus clinical malaria
 
% of children with positive mRDT result
 
% of mRDT-positive children prescribed an antimalarial
 
% of mRDT-negative malaria children prescribed an antimalarial
 
% of children with malaria prescribed the first line antimalarial
 

Screening for chronic conditions	
	
 
% of sick children tested for anemia
 
% of sick children assessed for malnutrition
 
% of sick children tested for HIV
 
% of children with anemia (severe and non-severe)
 
% of children with malnutrition (severe and moderate)
 
% of HIV-positive children
 

## 4 STUDY DESIGN

The primary intervention (i.e. ePOCT+) will be implemented using a parallel-group cluster non-randomized controlled superiority trial study design in two phases. In Phase 1 of the implementation, the medical content of the algorithm will be static. In Phase 2, the medical content of the algorithm will be modifiable according to the local data captured by ePOCT+ to date. Throughout Phases 1 and 2, mixed-methods operational research will be conducted to understand change in the quality of care, the implementation context, user and patient experience, and facilitators and barriers to the intervention at the individual, health facility and district levels.

### 4.1 Primary intervention

[figure not shown]
As part of the primary intervention in Phase 1, the ePOCT+ tool, as well as the complementary e-learning and supervision tools, will be provided to HWs of 42 PHC facilities in Rusizi and Nyamasheke districts of the Western Province in Rwanda for the management of sick children aged 1 day to 14 years (inclusive). The intervention will be implemented in blocks of 10-12 (half intervention and half control) HFs (**Figure 6**). Each step will last for four months, with the first month serving as a phase-in period. To assess the primary and secondary outcomes in Phase 1 (i.e. antibiotic prescription and cure rate), final decision on referral, diagnoses and treatments at initial consultation (day 0) will be recorded by HWs electronically in intervention and control facilities. All children in Phase 1 of the study will also be followed-up by a phone call or SMS (or home visit) to their caregiver at day 7 to determine their final health status. The CRFs are presented in **Appendix A**.

Due to the pragmatic nature of the study, the design is adaptive, in that changes to the implementation may be incorporated during each of the three parallel cluster studies to account for issues encountered in monitoring data and feedback from the field. These changes apply to the implementation context (such as training, frequency or focus of monitoring visits, etc.) and exclude significant adaptations of the algorithm.

The primary outcome (antibiotic prescription rate) will be compared between intervention and control facilities within implementation blocks (e.g. group 1 will be compared with group 2, group 3 with group 4, etc.). To assess the secondary outcome (cure rate), the data from all intervention periods (groups 1, 3 and 5) and control periods (groups 2, 4 and 6) will be combined to achieve a sufficient sample size. Additionally, HFs within the same group will also be compared longitudinally (e.g. outcomes during control and intervention periods can be compared in groups 2 and 4).

In Phase 2, the same outcome indicators as in Phase 1 will be measured and evaluated over time to monitor longitudinal changes in the effectiveness of the intervention. The medical content of the algorithm will not be fixed anymore, but rather modifiable. Each potential modification will first be evaluated by the Rwandan clinical expert group for its clinical coherence, safety and potential benefit and then applied to the retrospective data. If retrospective analyses confirm a clinically relevant positive impact (or resource saving), the modification will be implemented in the relevant locations and/or patient sub-groups.

Health facilities will need to demonstrate successfully meeting the objectives of Phase 1 before entering Phase 2. In case of any deviations from expected outcomes, or any issues that preclude reaching the study objectives as part of the parallel cluster study in Phase 1, design and implementation will be re-evaluated. In this case, Phase 1 would continue in modified form instead of moving on to Phase 2. Regardless of study phase, outcomes will be continuously monitored in all facilities, and if outcomes are not trending as expected, the causes will be investigated as part of routine monitoring of study implementation by the research team in collaboration with the DHMT.

**Figure 6:** Study design overview

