Statistical considerations	
For the parallel cluster study in Phase 1, the primary analysis will evaluate whether the use of ePOCT+ for case management of sick children in PHC facilities results in decreased antibiotic prescriptions (superiority analysis) at the initial consultation. Superiority in antibiotic prescription is defined as a relative decrease of <math>\geq 25\%</math> in the proportion of children prescribed an antibiotic. We estimated a cluster size of 660 patients (monthly utilization of 220 – accounting for up to 30% non-adherence from 315 – over 3 months) and an intraclass correlation coefficient of 0.025. To have 80% power to detect a 25% reduction in antibiotic prescription (e.g. from 35% to 26%), for a one-sided hypothesis test at alpha of 0.025, we would require a minimum of 11 clusters per arm. With 16 clusters (or HFs) per arm, over 3 months, we expect a total of 10,500 participants per arm, this sample size is sufficient to test for non-inferiority in the secondary outcome (clinical cure at day 7) between the control and intervention groups.
 
We will test for significant difference in the primary outcome of antibiotic prescription between study arms by comparing proportions and their 95% confidence intervals. Primary analysis of superiority will be performed according to the intention-to-treat principle. The results will be stratified by sex, age group (young infants ages 1 to 59 days, children aged 2 months to 5 years, and children aged 5 to 14 years), and select clinical variables (respiratory symptoms, fever without clinical source, gastrointestinal complaints, skin problems, ear and throat problems, anemia, and malnutrition).
 
At the estimated utilization of the PHC facilities in Nyamasheke and Rusizi districts, we anticipate that approximately 150,000 consultations will be conducted using ePOCT+ throughout the study.

Study duration and schedule	
Pilot phase: April 2021 – August 2021
 
Phase 1 (data collection): September 2021 – April 2022
 
Phase 2 (data collection): June 2022 – December 2022
 
Implementation research (data collection): October 2020 – October 2022
 
Sustainability assessment: August 2022 – December 2022

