3.1 Study design

The DYNAMIC RW Phase 1 study is a pragmatic, open-label two-arm parallel-group cluster non-randomized controlled superiority trial implemented in a sequential manner. There are three distinct implementation blocks of half intervention and half control health facilities that will be enrolled in the study at three sequential time points. The intervention consists of the provision to health workers of the ePOCT+ clinical decision support algorithm (CDSA), point-of-care tests proposed by ePOCT+ that are not part of routine care (pulse oximeter, CRP rapid test, additional hemoglobin cuvettes), complementary training on the tool, regular monitoring and mentorship/supervision visits by the study team and/or the District Health Management Team (DHMT). Mentorship and supervision will be enabled by a complementary dashboard (medAL-monitor), used to visualize and monitor study-related indicators.

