3.3 Sample size

The primary analysis will evaluate whether the use of ePOCT+ for case management of sick children in PHC facilities results in decreased antibiotic prescriptions (superiority analysis) at the initial consultation. Superiority in antibiotic prescription is defined as a relative decrease of $\geq 25\%$ in the proportion of children prescribed an antibiotic. We estimated a cluster size of 660 patients (monthly utilization of 220 – accounting for up to 30% non-adherence and/or loss to follow-up from 315 – over 3 months) and an intraclass correlation coefficient of 0.025. Non-adherence here is defined as HWs not using the application for all eligible patients that come to the HF for various reasons. To have 80% power to detect a 25% reduction in antibiotic prescription (from 35% to 26%), for a two-sided hypothesis test at alpha of

0.05, we would require a minimum of 11 clusters per arm. With 16 clusters per arm, over 3 months, we expect a total of 10,500 children in each study arm. Considering the pragmatic/adaptive nature of the study design, if a higher antibiotic prescription in the control arm is encountered (e.g. 45% or higher), each cluster study of 5-6 health facilities per study arm will be sufficiently powered to show a statistically significant reduction in the primary outcome. Sample size calculations were performed in R statistical software (version 4.0.3) using the CRTSize package (Rotondi, 2015).

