3.4 Statistical interim analyses

Interim analyses for the primary endpoints will be performed after each of the cluster studies. As previously mentioned, minor implementation changes may be made throughout the study to adapt to issues discovered from the monitoring data and feedback from the field at the time of the interim analyses. The Principal Investigators may decide to terminate the study prematurely according to certain circumstances, such as ethical concerns that cannot be resolved, in case of safety of the participants being compromised (e.g. if the benefits no longer outweigh the risks), alterations in accepted clinical practice that make the continuation of the study unwise, or evidence of harm of the intervention. In case of premature study termination, the Rwanda National Ethics Committee will be notified as per local guidelines.

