6.1 Analysis methods

Analyses will follow CONSORT guidelines (Campbell, Piaggio, Elbourne, & Altman, 2012; Piaggio et al., 2012; Schulz, Altman, & Moher, 2010; Zwarenstein et al., 2008). Outcomes will be described by arm using summary statistics. Baseline characteristics will be compared by study arm and by cluster study to ensure that the pragmatic allocation of health facilities and sequential rollout of the study did not introduce significant bias. Baseline characteristics which will differ between treatment arms within and over all clusters will be described using summary statistics.

Since the documentation of final treatment in both arms is part of the per protocol definition, only the PP population can be used for primary outcome analysis. The primary outcome will be evaluated using a random effects logistic regression model with the binary outcome variable of antibiotic prescription, with study arm and covariates at patient-level (e.g. age, sex) as fixed effects, and cluster (health facility) and patient included as random effects. Binary secondary outcomes will be evaluated in the same way. All estimates will be reported as odds ratios (ORs) with two-sided 95% confidence intervals (CI). The study will be deemed a success if antibiotic prescription at the initial consultation is 25% less in the ePOCT+ arm compared to the control arm, although we expect a greater reduction based on limited pilot data.

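### The plan does not say whether the within-block or the whole-trial comparison of antibiotic prescription is confirmatory, and it sets no level for block or interim tests

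*Protocol*

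**What the plan says.** - **Protocol 4.1** on the primary outcome: "The primary outcome (antibiotic prescription rate) will be compared between intervention and control facilities within implementation blocks". Its examples are group 1 against group 2 and group 3 against group 4. The next sentence combines groups 1, 3 and 5 and groups 2, 4 and 6, but only for cure.
- **Protocol 9.2** tests the primary outcome between study arms. Block appears there only as a heading for descriptive tables, and further detail is left to the SAP.
- **SAP 3.1**: "There are three distinct implementation blocks of half intervention and half control health facilities".
- **SAP 3.3** sizes the whole trial at 16 facilities per arm. It then makes a statement for the case of a control rate of at least 45%: "each cluster study of 5-6 health facilities per study arm will be sufficiently powered to show a statistically significant reduction in the primary outcome".
- **SAP 3.4**: "Interim analyses for the primary endpoints will be performed after each of the cluster studies". It gives no level or boundary, and does not say whether the looks are block-only or cumulative.
- **SAP 6.1**: "The primary outcome will be evaluated using a random effects logistic regression model with the binary outcome variable of antibiotic prescription". The model has an arm effect but no block term, and intervals are two-sided 95%. The success rule reads: "The study will be deemed a success if antibiotic prescription at the initial consultation is 25% less in the ePOCT+ arm". It names neither a test nor a data set.
- **Alpha** is given in three ways. SAP 3.3 is "for a two-sided hypothesis test at alpha of" 0.05, the protocol synopsis is "for a one-sided hypothesis test at alpha of 0.025", and Protocol 9.1 is one-sided at 0.05.

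**The concern.** Taken as written, Protocol 4.1 gives three separate tests of the primary outcome with no adjustment. SAP 3.3 treats significance in one block as a possible result, and SAP 3.4 looks at the endpoint after every block. SAP 6.1 describes something different, one model and one study-level success rule, but nothing withdraws Protocol 4.1.

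The choice of contrast could therefore be made after the data are seen. One significant block could be presented as superiority although the whole trial does not show it. Conversely, an effective intervention could be called inconsistent because some blocks miss significance. Both matter here: implementation may change between blocks, Protocol 4.1 makes meeting the Phase 1 objectives a condition for Phase 2, and Protocol 11.2 expects the results to support guidelines for national scale-up.

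**Working it through.** **Inputs.** From SAP 3.3: cluster size m = 660, ICC = 0.025, 35% against 26%, 80% power, 16 facilities per arm. From SAP 3.1 and 3.3: three blocks of separate facilities, 5-6 per arm, taken as 5, 5 and 6. Assumed, because no level is stated for them: each block or interim test at two-sided 0.05 (critical value 1.96), with independent blocks.

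**1. The plan's own figure.**
- Design effect = 1 + (660 − 1) × 0.025 = 17.475.
- n per arm without clustering = (1.960 + 0.842)² × (0.35×0.65 + 0.26×0.74) / 0.09² = 406.9.
- Clusters per arm = 406.9 × 17.475 / 660 = 10.8, so 11. This reproduces the stated minimum at two-sided 0.05, which is the same as one-sided 0.025.
- The same formula at one-sided 0.05, as in Protocol 9.1, gives 8.5, so 9. That alpha does not match the 11.

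**2. Error rate with no true effect.** Three independent tests give 1 − 0.95³ = 14.3%. In the benefit direction they give 1 − 0.975³ = 7.3%. The other rows come from simulating three independent block z-statistics and their information-weighted combinations (4 million draws).

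| Results allowed to carry a claim | Either direction | False benefit |
|---|---|---|
| Pooled final test only | 5.0% | 2.5% |
| Any of three blocks | 14.3% | 7.3% |
| Any block or pooled | 16.1% | 8.2% |
| Also a cumulative look after block 2 | 17.2% | 8.8% |

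A block is significant while the pooled test is not in 11.1% of such trials.

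**3. Power under the planned effect.** A 25% reduction from 35% is 26.25%. With k facilities per arm, SE = √[(0.35×0.65 + 0.2625×0.7375) × 17.475 / (660k)] and z = 0.0875 / SE.

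| k per arm | SE | z | Power |
|---|---|---|---|
| 5 | 0.0472 | 1.85 | 46% |
| 6 | 0.0431 | 2.03 | 53% |
| 16 (pooled) | 0.0264 | 3.31 | 91% |

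- All three blocks significant: 0.457 × 0.457 × 0.528 = 11%.
- At least one block significant: 1 − 0.543 × 0.543 × 0.472 = 86%.
- Pooled test significant while at least one block is not: 80% of trials (simulated).

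**4. The 45% statement in SAP 3.3.** A 25% reduction from 45% is 33.75%. For k = 5, z = 0.1125 / 0.0499 = 2.25 and power is 62%. For k = 6, z = 0.1125 / 0.0456 = 2.47 and power is 69%. For 80% power with 5 per arm, the rate must fall to about 31%: SE = √[(0.45×0.55 + 0.31×0.69) × 17.475 / 3300] = 0.0494, z = 0.14 / 0.0494 = 2.83, power 81%. That is a relative reduction of 0.14 / 0.45 = 31%.

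**The case against.** The strongest reply is that the documents lean towards one whole-trial test. Protocol 9.2 compares arms and defers to the SAP. SAP 3.5 sets one final analysis, SAP 6.1 has one model and one success sentence, and SAP 6.2 lists change in prescription across the three cluster studies as exploratory. The sample size needs at least 11 facilities per arm, which no block has. SAP 3.4 ties the interim looks to minor implementation changes, and its stopping reasons are ethics, safety, changed practice and harm, not efficacy. Protocol 4.1 might also be meant only to keep controls concurrent, which a block-stratified pooled test would do.

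Most of this stands. A reader might infer that the trial's type I error is 14-17%, or that the plan is silent on which test decides. The documents support neither:
- No level is given for block or interim tests, so 5% for each is an assumption.
- A block's comparison and its interim look may be the same test. The figure of about 17% needs a cumulative look after block 2, which is not specified.
- 14-17% counts false results in both directions, while the aim is superiority.
- The success rule is a 25% reduction, not a p-value. Over the whole trial with no effect and 35% in both arms, SE = √(2 × 0.35 × 0.65 × 17.475 / 10,560) = 0.0274, so an estimate that large is at z = 0.0875 / 0.0274 = 3.19, about 0.07% of trials.
- The 45% sentence in SAP 3.3 is a remark on power, not a decision rule. It does not say what reduction it assumes, and SAP 6.1 expects more than 25%.

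The reply does not remove the conflict. Protocol 4.1 contrasts block-wise comparison for the primary outcome with pooling for cure, and the SAP never withdraws it. The SAP itself foresees block-level significance, and no sentence ranks the contrasts.

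**Conclusion.** The concern holds as a conflict over which contrast is confirmatory, with block and interim tests left without a level. The inflation is conditional. If block results at two-sided 5% may carry a primary claim, the chance of at least one false significant result is 14.3%, or 16.1% with the pooled test added, and about 17% only with a cumulative second look. For false benefit the figures are 7.3%, 8.2% and about 9%, against 2.5%. If the pooled final test alone decides, it keeps its nominal level.

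The choice also matters when the intervention works: 91% power pooled, 46-53% per block, and 11% for all three blocks.

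The figures assume independent blocks of 5, 5 and 6 facilities per arm, the SAP's ICC and cluster size, and tests that hold their level. They leave aside bias from non-random allocation and the small number of facilities per block. The normal approximation flatters block power, since 5 per arm leaves only 8 degrees of freedom.

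**What to change.** 1. In Protocol 4.1 and SAP 6.1, state: *The sole confirmatory test of the primary outcome is the comparison of intervention with control over all three blocks, after block 3, at two-sided alpha 0.05, from the SAP 6.1 model with implementation block added as a fixed effect.* The block term keeps the comparison within block, as Protocol 4.1 intends. It uses two further degrees of freedom among 32 facilities.
2. In SAP 3.4 and Protocol 4.1, state: *Block-specific and interim estimates are descriptive, guide implementation only, and support no claim of superiority.*
3. Align the one-sided 0.025 in the protocol synopsis and the one-sided 0.05 in Protocol 9.1 with the SAP's two-sided 0.05, the level that yields the stated 11 clusters.
4. Reword SAP 3.3 so that a high observed control rate does not make a single block a basis for a primary claim. If the power remark is kept, give the reduction it assumes.

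The cost is wording and one model term, with no extra patients or data. The downside is that an early significant block result cannot be claimed as the primary finding.
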